
Study center(s)
 
The single-ascending dose (SAD) part in healthy adult subjects (Part A) will be conducted at 1 clinical study center in the United Kingdom. The multiple-ascending dose (MAD) part in patients with PH1 (Part B) is expected to take place at approximately 12 clinical study centers worldwide.

Objectives
 
Primary
 
 Evaluate the safety and tolerability of single- and multiple-ascending doses of ALN-GO1, respectively, in healthy adult subjects and in patients with PH1 
Secondary
 
 Characterize the pharmacokinetics (PK) of ALN-GO1 Evaluate the pharmacodynamics (PD) of ALN-GO1 
Exploratory
 
 ██████████ exploratory ██████████ ██

Study Design
 
This is a randomized, single-blind, placebo-controlled study of subcutaneously administered ALN-GO1. Subjects and patients will be randomized in a 3:1 ratio to receive either ALN-GO1 or placebo. The study is designed to evaluate the safety, tolerability, PK, and PD of single- and multiple-ascending doses of ALN-GO1 and will be conducted in 2 parts:
 
 Part A: SAD part in healthy adult subjects Part B: MAD part in adult and pediatric patients with PH1 
In Part A, subjects in each cohort will be randomized to receive 1 dose of ALN-GO1 or placebo.
 
In Part B, patients will be enrolled in up to 6 sequential dose cohorts to receive ALN-GO1 or placebo monthly or quarterly. Patients dosed monthly will receive 3 doses of ALN-GO1 or placebo in a blinded fashion. After completion of the blinded portion of the study, patients dosed monthly will be unblinded on or after Day 78. Patients who initially received placebo will then receive 3 doses of open-label ALN-GO1 dosed monthly at the same dose administered to the cohort into which they were initially randomized and will follow the same assessment schedule. Patients dosed quarterly will receive either ALN-GO1 or placebo on Day 1. All patients in quarterly dosing cohorts, including those initially randomized to placebo, will receive open-label ALN-GO1 on Day 85 at the same dose administered to the cohort into which they were initially randomized. Up to 2 expansion cohorts in

Part B may be enrolled based on available safety and PD data; these patients will all receive open-label ALN-GO1, not placebo.

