Important potential risks to healthy subjects and patients include injection site reactions (ISRs). Other potential risks include: embryofetal toxicity, coagulation abnormalities, and liver function test abnormalities. These potential risks have been reduced by the specific inclusion and exclusion criteria incorporated into the selection of healthy subjects as well as for patients with PH1 in this clinical study.

No data are available on the use of ALN-GO1 in pregnancy; however, human mutagenicity is not suggested based on the available nonclinical data (see Investigator's Brochure for further information). Embryofetal risk is limited by requiring that women of childbearing potential (WOCBP) must have a negative pregnancy test, cannot be breast feeding, and must be willing to use a highly effective method of contraception as specified in the protocol. Male subjects/patients are not required to use the contraception measures required for female study subjects/patients. No male contraception is considered to be required.

The occurrence of ISRs will be carefully monitored.

Nonclinical studies in rats showed mild to moderate decreases in fibrinogen and occasionally minimal prolonged prothrombin time without accompanying clinical or microscopic evidence of hemorrhage. This effect is likely species-specific as it was not observed in NHPs and will be monitored via clinical laboratory safety assessments.

As ALN-GO1 is a hepatically-targeted therapeutic, liver function tests will be carefully monitored. Nonclinical data suggest that there is a wide margin between the proposed clinical doses and any hepatic findings in toxicology studies and that any findings can be monitored. The potential non-specific, off-target risk of ALN-GO1 administration is considered to be low, based on nonclinical toxicological assessment of this molecule and accumulating experience with this RNA interference (RNAi) therapeutics platform.

During the course of this study, safety will be monitored by study Investigators, the Sponsor Medical Monitor, and a SRC. The initial dose level for administration in the MAD part of the study will have been previously shown to be safe, tolerable, and pharmacologically active based on SRC review of safety and PD data from the SAD part of the study. Stopping rules have also been designed to protect study participants.

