7.5.7.2. Eliciting and Recording Adverse Events

Eliciting Adverse Events

The patient should be asked about medically relevant changes in his/her health since the last visit. The patient should also be asked if he/she has been hospitalized, had any accidents, used any new medications, or changed concomitant medication routines (both prescription and OTC). In addition to patient observations, AEs will be documented from any clinically relevant laboratory findings, physical examination findings, ECG changes, or other findings that are relevant to patient safety.

Recording Adverse Events

The Investigator is responsible for recording non-serious AEs that are observed or reported by the patient after administration of the first dose of study drug regardless of their relationship to study drug through the end of study. Non-serious AEs will be followed until the end of study.

The Investigator is responsible for recording SAEs that are observed or reported by the patient after the time when the informed consent is signed regardless of their relationship to study drug through the end of study. SAEs will be followed until satisfactory resolution, until baseline level is reached, or until the SAE is considered by the Investigator to be chronic or the patient is stable, as appropriate.

All AEs must be recorded in the source records for the clinical study center and in the eCRF for the patient, whether or not they are considered to be drug-related. Each AE must be described in detail: onset time and date, description of event, severity, relationship to investigational drug, action taken, and outcome (including time and date of resolution, if applicable).

For purposes of this study, ISRs are considered to be Adverse Events of Clinical Interest. These AEs will be recorded both on a supplemental eCRF and on an Adverse Event of Clinical Interest form. Refer to the eCRF completion guidelines for details on these forms.

For SAEs, record the event(s) in the eCRF. If the EDC system is unavailable, complete the back-up SAE form.

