3.1.2 Multiple-ascending Dose Part in Patients with Primary Hyperoxaluria Type 1 (Part B)

Part B is the multiple-ascending dose part of the study in up to 24 adult and pediatric patients with PH1 with relatively well-preserved renal function. The overall allowable age range of the patients in Part B will be 6-64 years.

^a Patients in Part B will be invited to participate in an open-label extension study provided they meet the criteria described in Protocol ALN-GO1-001 Section 4.1.2 (Amendment 4; 27 June 2017).

Two mandatory ascending dose cohorts will be enrolled, with the possibility to also enroll up to 3 additional optional cohorts to further explore the optimal dose or regimen. Each cohort will be comprised of 4 patients, randomized 3:1 to ALN-GO1 or placebo. Up to 2 cohorts in Part B may be expanded by up to 4 additional patients (these patients will all receive ALN-GO1, not placebo).

Patients will be screened within 45 days prior to study drug administration. Baseline urinary oxalate excretion and creatinine clearance will be assessed through 24-hour urine collections. Patients will be randomized between Day -1 and Day 1 and will receive the first dose of ALN-GO1 or placebo on Day 1. The 24- and 48-hour postdose follow up assessments will take place on Day 2 and Day 3. Patients who receive study drug monthly will return to the clinical study center for safety, tolerability, PK, and PD monitoring at time points specified in the Schedule of Assessments (Protocol ALN-GO1-001 Table 2; Amendment 4, 27 June 2017) for the remaining 2 single-blind doses of study drug (through Day 57). After completion of the blinded portion of the study, patients dosed monthly will be unblinded (on or after Day 78). Patients who initially received placebo will then receive ALN-GO1 at the same dose administered to the cohort into which they were initially randomized and will follow the assessment schedule as indicated (Protocol ALN-GO1-001 Table 3; Amendment 4, 27 June 2017).

After the dosing period, patients will return to the clinical study center for continued safety, tolerability, PK, and PD monitoring through the last postdose follow-up visit. Following completion of the postdose follow-up period, patients will be invited to participate in an open-label extension study provided that:

- Urinary oxalate is above the ULN and patients meet at least 1 of the following criteria:
 - One 24-hour urinary oxalate value is >80% of baseline.

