7.2.1 Single-Blind Dosing Period

In Part B, Safety and PD data during the single-blind period will be summarized for the period starting from the first single-blind study drug date/time up to, and including, Study Day 85 for patients randomized to ALN-GO1, or prior to the first dose of ALN-GO1 for patients randomized to placebo. Patients receiving placebo in all regimen and dose cohorts will be pooled together.

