7.2.3 By-visit Data Presentation

In Part B, the by-visit PD and safety summaries will be presented according to the specifications below.

Monthly Dosing Regimen: Part B

Timepoint ^a	Placebo ^b	Monthly	Monthly	Monthly	Monthly	Monthly	Monthly
	(N=4)	ALN-GO1	ALN-GO1	ALN-GO1	ALN-GO1	ALN-GO1	ALN-GO1
		Single-blind ^c	Comb.d	Single-blind ^c	Comb.d	Single-blind ^c	Comb.d
		Dose1	Dose1	Dose2	Dose2	Total	Total
		(N=3)	(N=4 or 8)	(N=3)	(N=4 or 8)	(N=6)	(N=8 or 16)
Baselinee							
Day 29							
Day 57							
Day 85 ^f							
Day 113	NA						
Day 141	NA						
Day 169 ^g	NA						
Day 197 ^h	NA						
Day 225	NA						
Day 253	NA						
Day 281	NA						
Day 309	NA						

- a: In monthly dosing regimen, patients randomized to ALN-GO1 will be summarized by study day 1 to 85 during the single-blind monthly treatment period, then by post dosing follow-up period after Day 85 and up to Day 169, followed by Safety and PD follow-up after Day 169. Patients randomized to Placebo will be summarized by study day 1 to 85 relative to placebo dosing date during the single-blind treatment period. Data collected after the first dose of ALN-GO1 will be summarized separately by days relative to the first open-label ALN-GO1 dose with all visits for the rest of the study mirrored to the patients randomized to the single-blind ALN-GO1. These data will be summarized in combination with data from patients randomized to ALN-GO1 at each corresponding visit.
- b: Patients from all monthly and quarterly dosing cohorts randomized to placebo at study start
- c: Patients randomized to ALN-GO1 at study start receiving ALN-GO1 in single-blind manner
- d: Patients receiving ALN-GO1 in single-blind or open-label manner and in any sequence combined
- e: Baseline is defined as before first dose date/time of each treatment, placebo or ALN-GO1
- f: Day 85 is the end of treatment period
- g: Day 169 is the end of post-treatment follow-up period
- h: Day 197 and later visits are Safety and PD follow-up visits

Quarterly Dosing Regimen: Part B

Timepointa	Placebob	Quarterly	Quarterly	Quarterly	Quarterly	Quarterly	Quarterly	Quarterly	Quarterly	Quarterly
	(N=4)	2-doses ^c	1-dose ^d	Comb.e	2-doses ^c	1-dose ^d	Comb.e	2-doses ^c	1-dose ^d	Comb.e
		ALN-GO1	ALN-GO1	ALN-GO1	ALN-GO1	ALN-GO1	ALN-GO1	ALN-GO1	ALN-GO1	ALN-GO1
		Dose1	Dose1	Dose1	Dose2	Dose2	Dose2	Total	Total	Total
		(N=3)	(N=1)	(N=4)	(N=3)	(N=1)	(N=4)	(N=6)	(N=2)	(N=8)
Baselinef										
Day 29										
Day 57										
Day 85g										

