7.4.1 Adverse Events

In Part A, summary tables for AEs will be presented by ascending ALN-GO1 dose level, in total with all subjects receiving ALN-GO1, and placebo with subjects/patients receiving placebo pooled across enrollment cohorts presented first. AEs will be summarized separately for the single-blind dosing period and the study.

In Part B, for patients who were randomized to placebo, an AE during the single-blind period is defined as an AE with onset date/time on and after the first dose date/time of placebo and prior to the first dose date/time of open-label ALN-GO1. For patients who were initially randomized to ALN-GO1 a AE during the single-blind period is defined as an AE with onset date/time on or after the first dose date/time of ALN-GO1 and up to, and including, Study Day 85. AEs for single-blind period will be summarized by regimen and ascending dose level of ALN-GO1 and pooled placebo across regimen and dose being presented first. Sub-total for each regimen and overall will also be presented.

In Part B, a summary of AEs for the single-blind period will be provided by regimen and ascending dose level of ALN-GO1 and pooled placebo presented first. Total for each regimen and overall of ALN-GO1 will also be provided.

In Part B, for all patients receiving ALN-GO1, either as single-blind or open-label administration, and in any sequence, a AE is defined as an AE with onset date/time on or after the first dose date/time of ALN-GO1 and up to the end of study. All AEs under ALN-GO1 will be summarized by regimen and ascending dose, sub-total for each regimen, and for overall. At each dose level and for the sub-total and overall, AEs with be summarized for patients with single-blind administration only and then for single-blind and open-label administration combined.

In each analysis above, an overview of adverse events will be provided which summarizes subject-level incidence (frequency) of all AEs, drug-related AEs, grade 3/4/5 AEs, drug-related grade 3/4/5 AEs, treatment-emergent SAEs, drug-related treatment-emergent SAEs, and AEs leading to discontinuation of study drug and/or deaths.

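### If both regimens enrol, injection site reactions on monthly ALN-GO1 are set against a placebo group with fewer doses per patient, and no per-dose summary is planned

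*SAP*

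**What the plan says.** **Pooling.** SAP 7.2.1: "Patients receiving placebo in all regimen and dose cohorts will be pooled together". In the SAP 7.2.3 displays, the placebo column (N=4) in both the monthly and the quarterly table is footnoted as "Patients from all monthly and quarterly dosing cohorts randomized to placebo at study start". SAP 7.4.1 breaks single-blind adverse events down by regimen and dose of ALN-GO1, with "pooled placebo across regimen and dose being presented first". Protocol 8.2 also combines placebo patients from all cohorts.

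**Exposure.** The protocol synopsis states "Patients dosed monthly will receive 3 doses of ALN-GO1 or placebo in a blinded fashion" and "Patients dosed quarterly will receive either ALN-GO1 or placebo on Day 1". All quarterly patients then receive open-label ALN-GO1 on Day 85.

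**Windows.** Under SAP 7.2.1 and 7.4.1 the single-blind period runs through Day 85 inclusive for patients randomized to ALN-GO1. For placebo patients it stops before their first ALN-GO1 dose.

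**Counting.** SAP 7.4.1 reports the number and percentage of patients with an event. A patient counts once per system organ class and preferred term.

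**ISRs.** Protocol 1.5 places ISRs alone under important potential risks; embryofetal, coagulation and liver test risks are listed as other. Protocol 7.5.7.2 adds that "ISRs are considered to be Adverse Events of Clinical Interest" and has them recorded on a supplemental eCRF. The SAP does not mention ISRs or that eCRF. SAP 7.4.2 summarizes the number of injections for Part A only; Part B gets treatment duration and missed or interrupted doses.

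**The concern.** A reaction caused by an injection can occur only when an injection is given. The chance that a patient has at least one therefore depends on how many doses fall in the window. A monthly ALN-GO1 column holds only patients with three doses, whereas the placebo column mixes patients with three doses and patients with one. The two are not alike even if the drug adds nothing to the reaction rate of saline.

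At stake is the reading of the one risk that the protocol calls important, in the tables that set each regimen beside placebo. No planned summary uses doses or injections as the denominator, so the tables themselves do not let a reader separate a drug effect from a count of doses.

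**Working it through.** **Step 1: reproduce the placebo N.** SAP 3.1.2: "Each cohort will be comprised of 4 patients, randomized 3:1 to ALN-GO1 or placebo". That is one placebo patient per cohort. The SAP 7.2.3 displays have two monthly and two quarterly dose groups, so placebo N = 2 + 2 = 4, as the SAP shows. Two of these patients have three blinded doses and two have one.

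**Step 2: expected incidence with no drug effect.** Let p be the ISR risk per dose, the same for ALN-GO1 and saline. The documents give no value, so p is assumed over a range. With independent doses, incidence after k doses is 1 − (1 − p)^k.

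| p | Monthly, k=3 | Quarterly, k=1 | Pooled placebo (mean of the two) | Monthly − placebo | Quarterly − placebo |
|---|---|---|---|---|---|
| 0.10 | 27.1% | 10.0% | 18.55% | +8.55 | −8.55 |
| 0.20 | 48.8% | 20.0% | 34.4% | +14.4 | −14.4 |
| 0.30 | 65.7% | 30.0% | 47.85% | +17.85 | −17.85 |

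**Step 3: the Day 85 dose.** The last column counts only the Day 1 dose. If reactions to the second quarterly dose also count, k = 2:

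- p = 0.10: 1 − 0.9² = 19.0%, against 18.55%, +0.45 points.
- p = 0.20: 1 − 0.8² = 36.0%, against 34.4%, +1.6 points.
- p = 0.30: 1 − 0.7² = 51.0%, against 47.85%, +3.15 points.

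Full counting is an upper limit, because the window closes at the end of Day 85. The quarterly difference at p = 0.20 thus lies between −14.4 and +1.6.

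**Step 4: the overall ALN-GO1 column.** Allocation is 3:1 in every randomized cohort, so the regimen mix is the same in the ALN-GO1 total as in placebo. At p = 0.20 the total is (6 × 48.8% + 6 × 20.0%)/12 = 34.4%, a gap of 0. If Day 85 reactions count in full, it is (6 × 48.8% + 6 × 36.0%)/12 = 42.4%, a gap of +8.0. That gap comes from the window, not from pooling.

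**Step 5: sensitivity of the monthly gap at p = 0.20.**

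- Placebo mix: with 4 monthly and 1 quarterly, pooled placebo is (4 × 48.8% + 20.0%)/5 = 43.04%, gap +5.8. With 1 and 4 it is (48.8% + 4 × 20.0%)/5 = 25.76%, gap +23.0. With monthly patients only, the gap is 0.
- Within-patient correlation ρ (beta-binomial, a = p(1−ρ)/ρ, b = (1−p)(1−ρ)/ρ): the chance of no reaction in three doses is b(b+1)(b+2)/[(a+b)(a+b+1)(a+b+2)]. At ρ = 0.2 this is 3.2 × 4.2 × 5.2/(4 × 5 × 6) = 0.582, gap 10.9 points with the 2 + 2 mix. At ρ = 0.5 it is 0.8 × 1.8 × 2.8/(1 × 2 × 3) = 0.672, gap 6.4. At ρ = 1 the gap is 0.

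**Step 6: noise.** For 6 monthly ALN-GO1 patients against 4 placebo patients at p = 0.20, the standard error is √[0.488 × 0.512/6 + (2 × 0.488 × 0.512 + 2 × 0.2 × 0.8)/16] = 0.305, about 30 points.

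**Step 7: per-dose rate.** With the 2 + 2 mix, placebo has 2 × 3 + 2 × 1 = 8 doses, monthly ALN-GO1 6 × 3 = 18 and quarterly ALN-GO1 6 × 1 = 6 (Day 1 only). Expected reactions per dose equal p in every column, so the artificial gap is 0.

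**The case against.** The strongest reply is that the effect is conditional and small beside the noise. Part B starts with dosing every 28 days and the further cohorts are optional, so placebo patients in both regimens are not guaranteed. One placebo patient out of four is 25 points, and the standard error is about 30. The study is descriptive, without hypothesis tests or a power basis, and pooling is understandable with one placebo patient per cohort. The listings of adverse events and of study drug administration would let a reader rebuild per-dose rates for at most 24 patients. All of this stands and limits the weight of the point. It does not make the planned monthly comparison like for like, and a rate rebuilt by hand is not a planned summary.

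A reader might also infer that the tables favour quarterly dosing. The documents do not settle that, because the ALN-GO1 window takes in Day 85 while the placebo window stops before the first ALN-GO1 dose. The SAP 7.2.3 footnotes to the quarterly table treat the Day 85 dose as open-label, yet 7.2.1 and 7.4.1 do not exclude reactions to it.

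Nor do the documents support the inference that the choice of regimen would be misled. In-study regimen decisions rest with an unblinded Safety Review Committee reviewing accumulating data, the primary SAP analysis follows completion of all follow-up, and comparing monthly with quarterly ALN-GO1 does not use placebo. More dosing visits are also a real feature of monthly treatment, so patient-level incidence should stay beside any per-dose rate.

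**Conclusion.** The point holds with conditions. If both regimens enrol, the regimen-specific single-blind tables overstate ISR incidence on monthly ALN-GO1 relative to placebo, in expectation and with no drug effect. The excess is about 9 to 18 points for an assumed per-dose risk of 10% to 30%, independent doses and a 2 + 2 placebo mix. It shrinks with within-patient correlation. It is zero if only one regimen enrols or if reactions are wholly determined by the patient.

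The direction for quarterly ALN-GO1 cannot be stated: at 20% per dose it is about −14 points if only Day 1 counts and about +2 if Day 85 reactions count in full. It would be wrong to conclude that the safety comparison as a whole is biased by pooling, because the overall ALN-GO1 total has the same regimen mix as placebo. The absence of any ISR or per-dose summary for the only risk listed as important is a plain gap, whichever cohorts enrol.

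**What to change.** In SAP 7.4.1, add one ISR table drawing on the supplemental eCRF: patients with any ISR, and ISRs per dose administered (also per injection where a dose uses more than one), by regimen and dose of ALN-GO1, with placebo shown by regimen and pooled. Base the comparison with placebo on the per-dose figure. Keep the pooled tables and the patient-level incidence.

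In SAP 7.2.1, state that adverse events with onset after the Day 85 dose in quarterly patients belong to the open-label period, and carry the same wording into 7.4.1.

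This is a cheap improvement: SAP wording and one table, from data the protocol already collects. The downside is very small placebo denominators, about two patients per regimen in the displayed design, so the table should show counts and doses beside every rate.

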7.2.3 By-visit Data Presentation

In Part B, the by-visit PD and safety summaries will be presented according to the specifications below.

Monthly Dosing Regimen: Part B

Timepoint ^a	Placebo ^b	Monthly	Monthly	Monthly	Monthly	Monthly	Monthly
	(N=4)	ALN-GO1	ALN-GO1	ALN-GO1	ALN-GO1	ALN-GO1	ALN-GO1
		Single-blind ^c	Comb.d	Single-blind ^c	Comb.d	Single-blind ^c	Comb.d
		Dose1	Dose1	Dose2	Dose2	Total	Total
		(N=3)	(N=4 or 8)	(N=3)	(N=4 or 8)	(N=6)	(N=8 or 16)
Baselinee							
Day 29							
Day 57							
Day 85 ^f							
Day 113	NA						
Day 141	NA						
Day 169 ^g	NA						
Day 197 ^h	NA						
Day 225	NA						
Day 253	NA						
Day 281	NA						
Day 309	NA						

- a: In monthly dosing regimen, patients randomized to ALN-GO1 will be summarized by study day 1 to 85 during the single-blind monthly treatment period, then by post dosing follow-up period after Day 85 and up to Day 169, followed by Safety and PD follow-up after Day 169. Patients randomized to Placebo will be summarized by study day 1 to 85 relative to placebo dosing date during the single-blind treatment period. Data collected after the first dose of ALN-GO1 will be summarized separately by days relative to the first open-label ALN-GO1 dose with all visits for the rest of the study mirrored to the patients randomized to the single-blind ALN-GO1. These data will be summarized in combination with data from patients randomized to ALN-GO1 at each corresponding visit.
- b: Patients from all monthly and quarterly dosing cohorts randomized to placebo at study start
- c: Patients randomized to ALN-GO1 at study start receiving ALN-GO1 in single-blind manner
- d: Patients receiving ALN-GO1 in single-blind or open-label manner and in any sequence combined
- e: Baseline is defined as before first dose date/time of each treatment, placebo or ALN-GO1
- f: Day 85 is the end of treatment period
- g: Day 169 is the end of post-treatment follow-up period
- h: Day 197 and later visits are Safety and PD follow-up visits

Quarterly Dosing Regimen: Part B

Timepointa	Placebob	Quarterly	Quarterly	Quarterly	Quarterly	Quarterly	Quarterly	Quarterly	Quarterly	Quarterly
	(N=4)	2-doses ^c	1-dose ^d	Comb.e	2-doses ^c	1-dose ^d	Comb.e	2-doses ^c	1-dose ^d	Comb.e
		ALN-GO1	ALN-GO1	ALN-GO1	ALN-GO1	ALN-GO1	ALN-GO1	ALN-GO1	ALN-GO1	ALN-GO1
		Dose1	Dose1	Dose1	Dose2	Dose2	Dose2	Total	Total	Total
		(N=3)	(N=1)	(N=4)	(N=3)	(N=1)	(N=4)	(N=6)	(N=2)	(N=8)
Baselinef										
Day 29										
Day 57										
Day 85g										
Day 113 ^h	NA			NA			NA			NA
Day 141	NA			NA			NA			NA
Day 169 ⁱ	NA			NA			NA			NA
Day 197 ^j	NA			NA			NA			NA
Day 225	NA			NA			NA			NA
Day 253	NA			NA			NA			NA
Day 281	NA			NA			NA			NA
Day 309	NA			NA			NA			NA

- a: In quarterly dosing regimen, patients randomized to ALN-GO1 will be summarized during the treatment period by study days with ALN-GO1 dosing on Day 1 (single-blind) and 85 (open-label) followed by the Safety and PD follow-up period after Day 169. Patient randomized to Placebo will be summarized by days relative to placebo dosing date for the placebo period (Study Days 1-85), and separately by days relative to the open-label ALN-GO1 dosing date for the treatment period (Days 85-169 post placebo dose; Days 1-85 post ALN-GO1 dose), followed by the Safety and PD follow up period after Day 169.
- b: Patients from all monthly and quarterly dosing cohorts randomized to placebo at study start
- c: Patients randomized to ALN-GO1 at study start. First quarterly GO1 dose is in single-blind manner and the second quarterly GO1 dose is in open-label manner
- d: Patients randomized to placebo at study start and received one dose of open-label ALN-GO1 on Day 85, and Days are relative to the open label ALN-GO1 dose.
- e: Patients receiving ALN-GO1 in single-blind or open-label manner and in any sequence combined.
- f: Baseline is defined as xxxx before first dose date/time of each treatment, placebo or ALN-GO1
- g: Day 85 is the end of single-blind treatment period for placebo and 2-doses ALN-GO1 patients, and the end of open-label ALN-GO1 treatment period for 1-dose ALN-GO1 patients
- h: Day 113 and later visits are Safety and PD follow-up period for 1-dose ALN-GO1 patients
- i: Day 169 is the end of open-label treatment period for 2-doses ALN-GO1 patients
- j: Day 197 and later visits are Safety and PD follow-up period for 2-doses ALN-GO1 patients

